Test-Case Protocol

Version 2, July 31, 2020

R2-B5 -Synthetic Mid-Urethral Slings for Stress Urinary Incontinence in Women

Protocol

National Evaluation System for health Technology coordinating center (NESTcc) ID

Number: [R2-B5]

Lead Principal Investigator: [[name], MS, MPH]

Sponsor: [FDA]

Funded by: Center for Devices and Radiological Health – FDA

Version Number: 2.0

Date: 31 July 2020

TABLE OF CONTENTS

PROTOCOL SYNOPSIS	4
1. INTRODUCTION	6
1.1 RATIONALE & BACKGROUND	6
2. STUDY COLLABORATORS	8
2.1 CONTRIBUTING INSTITUTIONS & ROLES	8
3. STUDY OBJECTIVES	9
4. STUDY DESIGN	10
5. TARGET POPULATION	11
6. STUDY PROCEDURES	11
6.1 STUDY DURATION AND TIMELINE	13
6.2 PROTOCOL DEVIATION HANDLING	13
7. STUDY OUTCOMES	13
8. DATA QUALITY	13
8.1 DATA COLLECTION AND MANAGEMENT	14
8.2 MONITORING PLANS	15
9. STATISTICAL ANALYSIS PLAN (SAP)	15
9.1 STATISTICAL METHODS	15
10. STUDY ADMINISTRATION	15
10.1 CONSENT AND HIPAA AUTHORIZATION REQUIREMENTS	15
10.2 RISK/BENEFIT ASSESSMENT	16
11. RESULTS DISSEMINATION	16
12. REFERENCES	17
13. APPENDICES	19

PROTOCOL SYNOPSIS

Protocol Number: Protocol Date:	R2-B5 07/31/2020
Test-Case ID/Title:	Synthetic Mid-Urethral Slings for Stress Urinary Incontinence in Women
Investigator(s): Study Description:	[name], MS, MPH This project seeks to better understand the safety of mesh mid-urethral slings used for stress urinary incontinence by leveraging electronic health record data. The FDA intends on incorporating these data into its growing portfolio of evidence in order to help support regulatory decision making on level of risk for these procedures and recommendations around use of synthetic mesh for this indication. This study has the potential to increase medical knowledge regarding these devices. A detailed schematic describing all assessments is included in Section 6, Study Procedures .
Summary and Objectives:	The objectives of this project are to assess the capacity of routinely collected electronic health record data to be used to evaluate mid-term (>1 years) to long-term (>2 years) adverse events following transvaginal synthetic surgical mesh implantation (mid-urethral slings) for female stress urinary incontinence (SUI).

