However, by the mid-2000's, a growing number of adverse event reports had been submitted to the MAUDE FDA database related to trans-vaginal synthetic mesh products used for these indications. During 2005-2010, MAUDE received 1371 reports of injury, death, and malfunction of mesh for SUI treatment, related to mesh erosion, pain, infection, recurrence of urinary symptoms, and organ perforation, along with a 5-fold increase in MAUDE reporting rates in 2008-2010 compared to 2005-2007. While these numbers increased scrutiny surrounding these devices, a lack of denominator data and a reliance on voluntary reporting that is sensitive to FDA and press scrutiny limit the interpretability of these findings.

Risk assessments around synthetic surgical mesh for SUI remains uncertain for some outcomes extending beyond one year²⁵. [name] and colleagues evaluated a New York State prospective registry (SPARC) that included all surgeries and evaluated 41,604 women undergoing mesh implantation for pelvic organ prolapse or stress urinary incontinence. Among the 22,252 women undergoing surgery for SUI, 1.6% of them had mesh erosions that required intervention²². In one UK study, overall re-operation rates were only 3.2% among mid-urethral sling procedures for SUI after a median 2.8 years of follow-up²⁶. In a private US claims database, the cumulative re-operation rate was 14.5% after a median 9 years of follow-up²⁷, with sling revision/removal at 3.7%²⁸. Other small studies in non-US populations have shown low rates of long-term complications (1-3%)²⁹. A recent UK study among 95,057 women and a median follow-up time of 5.5 years found that risk of re-operation was 2.6% at 1 year, 5.5% at 5 years, and 6.9% at 9 years³⁰. More specifically, mesh removal rates were 3.3% at 9 years in this population. Another UK study among 92,246 patients with first time mesh implantations for SUI found a 5-year complication rate of 9.8%³¹. A Canadian study of 59,887 women found ~3.5% may require mesh removal or revision within 10 years of initial surgery³².

There have also been some systematic reviews and meta-analyses done attempting to further understand the complications in this population. In 2015, a systematic review of studies with a follow-up of 36 months for TOMUS and 60 months for RPMUS were searched and studies comparing the two were

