included (49 studies, 11 RCT, 38 retrospective cohort studies)³³. The studies had a complication rate of 193% for RPMUS and a complication rate of 23.8% in TOMUS surgeries. The two approaches had similar objective cure rates, but TOMUS had a lower subjective cure rate than RPMUS. In 2017, a review was published evaluating 11 RCTs and 5 non-RCTs evaluating the long term efficacy and safety of MUS in women³⁴. There was a total of 1,200 patients across 11 RCTs with individual surgical approach populations in each trial being in the 30-299 range. Ascertainment for the RCTs were good and showed no safety or efficacy differences between approaches but were limited in size, and the non-RCTs were similarly limited in size (5206 patients across 5 studies). The most recent review, in 2019, evaluated a total of 175 RCTs with 21,598 women, and noted that most studies had high or unclear risk of bias across all Cochrane domains³⁵. A network metanalysis was done from 105 trials that reported cure and 120 trials that reported improvement of symptoms, and across the 4 common surgical approaches for MUS. The key findings from this meta-analysis was that RPMUS, TOMUS, traditional sling, and open colposuspension were more effective than other procedures for SUI, but that data on long term effectiveness and adverse events were limited, particularly around comparison between MUS and non-MUS procedures. Other relevant articles are referenced here as well, but almost all of these also cite limitations in sample size, data bias collection, and evidence limitations³⁶⁻⁴¹.

The FDA is very interested in measuring the risk of mesh use for SUI for longer outcomes >1 year within electronic health record data, which are collected for routine care and can be accessed for a variety of surveillance activities. For this reason, NESTcc was approached by the FDA to engage in a collaborative consortium to pursue these concerns, and an RFP was released to study this within an electronic health record environment in which it is hoped that longer term outcomes can be ascertained. Multiple academic medical centers, including Vanderbilt University Medical Center, Yale New Haven Health System, Weill-Cornell, Mayo Clinic, and Lahey Hospital & Medical Center, were recruited to collect and analyze patient data regarding mesh implantations for SUI for the outcomes of re-operation, mesh erosion, all-cause chronic pain, and continued voiding symptoms that occur past 1 year after the surgery.

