3. STUDY OBJECTIVES

There remains uncertainty with regards to longer term outcomes among women receiving mesh slings for stress urinary incontinence, and this project seeks to address knowledge gaps for long term outcomes among mesh implantations by leveraging electronic health record data across 5 participating health systems.

Specific Aims: This project seeks to provide a proof of concept for post-market medical device surveillance by assessing the capacity of routinely collected electronic health record data to evaluate the long-term adverse outcomes related to synthetic surgical mesh implantation for stress urinary incontinence.

In pursuit of this goal, this project will:

- 1) Assess data element availability among key covariates and exposures among patients undergoing surgery for stress urinary incontinence,
- 2) If data are available, to assess rates of outcomes of mesh erosion, re-operation for SUI, reoperation for mesh revision or removal, chronic pain either as a new or worsening pain or requiring re-operation and voiding symptoms either as a new symptom or requiring reoperation, each with extended surveillance windows after surgery.
- 3) Specifically, this project will evaluate mid-term (>1 year) and long-term (>2 years) adverse events following synthetic surgical mesh implantation (mid-urethral slings) for female SUI.
- 4) Lastly, if the data quality and volume are sufficient, we will develop a risk prediction model for the risk of the each of the outcomes stated above among patients receiving mesh for SUI.

In summary, this project seeks to better understand the safety of mesh used for stress urinary incontinence by leveraging electronic health record data. The FDA intends on incorporating these data into its growing portfolio of evidence in order to help support regulatory decision making on level of risk

for these procedures and recommendations around use of mesh for this indication. This study has the potential to increase medical knowledge regarding these devices.

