7. STUDY OUTCOMES

The primary outcomes of interest are:

- Re-operation (revision, incision, excision, removal) or mesh removal
- Chronic pain, defined as pain persisting at least three months after surgery⁴⁹
- Voiding symptoms, defined as recurrence of incontinence or new retention.

All outcomes are determined in the surveillance period after surgery. Re-operation or mesh removal is defined as a surgery for any kind of mid-urethral sling, urethral bulking agent, bladder neck pubovaginal sling (autologous or allograft), or revision for mesh exposure. Resumption of voiding symptoms was defined as subsequent urinary retention, urinary incontinence, and sling revision for urinary retention. Chronic pain is defined as a new post-operative pain score >3 of 10 on vital sign data occurring over at least 3 months or greater of duration, or diagnosis codes related to abdominal and pelvic pain.

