9. STATISTICAL ANALYSIS PLAN (SAP)

9.1 STATISTICAL METHODS

Each of the outcomes, exposures, and covariates will be analyzed for counts at each site and a summarization and report will be provided to characterize the data. Stratified reporting of those receiving surgery for SUI with mesh and those without mesh will be performed. While this will allow for indirect comparison of these sub-populations side by side, no direct statistical comparisons between the groups will be made.

Next, if the characterization of the data is sufficient for the task, we will pursue a Cox proportional hazards model analysis, with each of the outcomes assessed from the time of the surgery as a time-to-event. We will censor the time-to-event analysis with death or loss to follow-up, defined as a time period >2 years from last applicable encounter of primary care, Obstetrics & Gynecology, or Urology. The models will be executed at each institutional separately using LASSO Cox to determine the consistently included covariates in each institution²⁵. We will then use the final variable list and utilize the method described by Lu and colleagues that uses a distributed analysis approach to obtain an exact model solution without sharing case level data (only intermediate and aggregate model coefficients and matrices)⁴⁶.

Because bootstrapping combined with the distributed analysis method would be computationally intensive, we will utilize 10-fold cross validation across all sites for internal validation of the risk model. We will assess overall discrimination using Harrell's concordance statistic (C-statistic)⁴⁷. To provide calibration assessments, we will also evaluate the model at fixed time points of 1 year and 2 year for each outcome using the AUC and the Estimated Calibration Index (ECI)⁴⁸. The ECI looks at the squared difference between the predicted probability and an estimated observed probability, ranging between 0 and 100, with 0 meaning perfect calibration. Additionally, we will graphically analyze calibration by investigating the smoothed observed-to-predicted probability plot⁴⁸.

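### The aims are rates of adverse events beyond 1 and 2 years, but Section 9.1 specifies only counts and a Cox model from surgery, never separates late from early events, and stops its fixed-time checks at 2 years

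*Protocol*

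**What the plan says.** **Target period.** The synopsis sets the objective as "mid-term (>1 years) to long-term (>2 years) adverse events". Aim 3 in Section 3 repeats it: "this project will evaluate mid-term (>1 year) and long-term (>2 years) adverse events following synthetic surgical mesh implantation". Section 1.1 describes the outcomes in the same way, ending with "continued voiding symptoms that occur past 1 year after the surgery".

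**Measure.** Aim 2 in Section 3 undertakes "to assess rates of outcomes of mesh erosion, re-operation for SUI" and the other outcomes, over extended windows after surgery. No section gives the start or end of those windows. Section 7 says only: "All outcomes are determined in the surveillance period after surgery".

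**Analysis.** Section 9.1 starts with a descriptive step: "Each of the outcomes, exposures, and covariates will be analyzed for counts at each site", reported separately for women with and without mesh. If the data prove adequate, a Cox model follows for each outcome. Time runs from surgery, and censoring is at death or loss to follow-up. Performance is assessed by Harrell's C overall, by a smoothed calibration plot, and at two fixed times: the team will "evaluate the model at fixed time points of 1 year and 2 year for each outcome using the AUC and the Estimated Calibration Index". The synopsis and Sections 4 and 6 repeat the modelling plan with the same two times.

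**The concern.** Section 1.1 gives the reason for the study: results to one year were thought reasonable, and later data were sparse. The later period is therefore what the analysis has to estimate. A risk predicted at 1 year covers years 0 to 1 and contains no event from the mid-term period. A risk predicted at 2 years covers years 0 to 2 and contains no event from the long-term period. The plan states no landmark analysis, no rate by period and no fixed evaluation time beyond 2 years.

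The descriptive step has a related weakness. Aim 2 promises rates, but Section 9.1 names only counts, without person-time or cumulative incidence. Eligible surgeries run from 2010 to 2019 (Section 5), and one site's data begin in 2013 (synopsis), so follow-up differs widely between women and between sites. The Cox model is conditional on data quality, so the counts may be the only result delivered for Aims 2 and 3. Section 9.1 expects readers to set the mesh and non-mesh groups side by side, and the sponsor intends to use the results in regulatory decisions.

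**Working it through.** The protocol states no event count or precision target on this point, so there is no figure to reproduce. The check has two parts.

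**1. Aim against stated analysis**

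| Planned output | Period covered | Isolates >1 year? | Isolates >2 years? |
|---|---|---|---|
| Counts by site and mesh group | After surgery, window undefined | No | No |
| Cox model | From surgery to death or loss | Late events included, not separated | Late events included, not separated |
| Harrell's C | All follow-up, pooled | No | No |
| AUC and ECI at 1 year | 0 to 1 year | Contains none | Contains none |
| AUC and ECI at 2 years | 0 to 2 years | Mixed with year 1 | Contains none |
| Smoothed calibration plot | No horizon stated | Not stated | Not stated |

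**2. Illustration of size**

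Inputs: one external study cited in Section 1.1 gives "risk of re-operation was 2.6% at 1 year, 5.5% at 5 years, and 6.9% at 9 years". Write F(t) for cumulative risk, so F(1) = 2.6%, F(5) = 5.5% and F(9) = 6.9%. F(2) is not given. A constant hazard from year 1 to year 5 gives F(2) = 3.33%. Linear interpolation gives almost the same value: 2.6 + (5.5 − 2.6)/4 = 3.325%. Because F cannot decrease, F(2) must lie between 2.6% and 5.5%.

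- Share of 2-year risk arising in year 1, F(1)/F(2): 2.6/3.33 = 78%. Range: 2.6/5.5 = 47% to 2.6/2.6 = 100%.
- Share of 9-year re-operations after year 2, (F(9) − F(2))/F(9): (6.9 − 3.33)/6.9 = 52%. Range: (6.9 − 5.5)/6.9 = 20% to (6.9 − 2.6)/6.9 = 62%.
- Share of all events to 5 and 9 years arising in year 1: 2.6/5.5 = 47% and 2.6/6.9 = 38%.
- Average yearly hazard, −ln[(1 − F(t))/(1 − F(s))]/(t − s): 2.6% in year 1, 0.76% in years 1 to 5 and 0.37% in years 5 to 9. Year 1 is about 3.5 and 7 times the two later rates.
- Landmark risk among women event-free at 1 year, (F(t) − F(1))/(1 − F(1)): 2.9/97.4 = 2.98% to year 5 and 4.3/97.4 = 4.41% to year 9. Counted from surgery, the figures are 5.5% and 6.9%.
- Landmark risk among women event-free at 2 years, with F(2) = 3.33%: 2.17/96.67 = 2.2% to year 5 (range 0% to 2.98%) and 3.57/96.67 = 3.7% to year 9 (range 1.48% to 4.41%).

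The same curve shows what unequal follow-up does to crude counts. Two groups with identical risk, one followed for 1 year and the other for 5, would show 2.6% and 5.5%, a ratio of 5.5/2.6 = 2.1 that comes only from length of follow-up.

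**The case against.** Several stronger readings are tempting, and the protocol does not support them.

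- *That the models are checked only at 1 and 2 years.* Section 9.1 also plans Harrell's C and a calibration plot. The Cox model has no 2-year cap, so later events enter both the fit and the C-statistic. What remains is that C is a rank measure pooling early and late events, and that the plot has no stated horizon. Neither is specified as a check of absolute risk beyond 2 years.
- *That the output mostly restates the first year.* On the cited curve this is plausible only for the 2-year check. With full follow-up to 5 or 9 years, the year-1 share is 47% or 38%.
- *That counts are the planned rate estimate.* The sentence on counts covers exposures and covariates too and describes data characterisation. The accurate statement is that rates are promised and Section 9.1 names no estimator for them.
- *That Section 7 starts the clock on the day of surgery.* It refers to the period after surgery without giving a start, and chronic pain has a three-month duration. The defect is an undefined window.
- *That women operated on in 2019 have under a year of follow-up.* The synopsis gives 2010–2019 for data capture but also allows the most recent data available, and the study runs to March 2021. The cut-off is ambiguous. Unequal follow-up does not depend on it.

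Two broader defences carry some weight. The project is a proof of concept with conditional aims, and it excludes any direct comparison of mesh with non-mesh, so unequal follow-up biases no planned test. Aim 3 is nevertheless a stated aim, and side-by-side reading is expected. A separate analysis plan may exist and could name an estimator. But Section 9 is itself headed as the statistical analysis plan, and it positively sets the surgery time origin and the 1- and 2-year times. This is more than detail left for later.

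**Conclusion.** The concern holds as a mismatch between aim and method. No analysis in the protocol isolates events after 1 year, the extended windows are undefined, and no fixed-time AUC or ECI reaches the period beyond 2 years. Rates are promised, but only counts are specified, over follow-up that differs by year of surgery and by site.

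On the cited re-operation curve, about 78% (47% to 100%) of the risk assessed at 2 years arises in year 1, and about 52% (20% to 62%) of 9-year re-operations lie beyond the last fixed evaluation time. These sizes are illustrative. They rest on one external curve and an assumed 2-year risk of 3.3%, and they apply to re-operation only. Nothing in the protocol allows the same calculation for chronic pain or voiding symptoms. The mismatch itself depends on none of these numbers.

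**What to change.** Make these changes in Section 9.1, and define the windows in Sections 3 and 7:

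1. For Aims 2 and 3, report cumulative incidence with 95% confidence intervals at stated horizons from surgery, with at least one beyond 2 years (for example 1, 2 and 5 years). Report by site, by mesh and non-mesh, and by surgical approach. The synopsis already plans strata by approach, but Section 9.1 omits them.
2. Add landmark estimates: among women event-free and under follow-up at 1 year, and again at 2 years, the risk to a stated later horizon.
3. Add at least one AUC and ECI evaluation time beyond 2 years where follow-up supports it, and state the horizon of the calibration plot.

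The particular later horizon is for the study team to choose from the follow-up available; the protocol does not imply 5 years. The cost is modest programming on data already being collected. Intervals will be wider at later horizons, where fewer women remain under observation.

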10. STUDY ADMINISTRATION

10.1 CONSENT AND HIPAA AUTHORIZATION REQUIREMENTS

A waiver of consent will be applied for because consent human subjects is not required. There is no patient contact, and the data will be obtained from electronic health records through database queries and search queries are performed according to the project's study procedures defined in this document. Searches are logged and will be audited. De-identified datasets are exported directly from the system into a statistical/analysis program. As no HIPAA identifiers are available in the database, and the proposed project does not plan to re-identify these records, this study meets criteria for non-human subject's research and involves no more than minimal risk and with security measures to protect the privacy and security of the data in place.

There are minimal potential risks to the human subjects. The study proposes to examine electronic medical records of patients. Patients will not be exposed to study materials or protocols; only electronic

medical records will be abstracted retrospectively with the IRB approval in place. Though there is a slight risk of loss of confidentiality or privacy of these subjects, all data will reside within the hospital firewall. The proposed study does not involve any interventions or alternative treatments.

Nonetheless, to ensure confidentiality and appropriate use of the database, all relevant key personnel for this study will enter into a data use agreement, which prohibits any use of the data not described in this protocol, including the re-identification of the database records. Since this study involves no more than minimal risk and with security measures to protect the privacy and security of the data in place noted above, it will not adversely affect the rights and the welfare of the patients in the database.

10.2 RISK/BENEFIT ASSESSMENT

This study is beneficial because it is seeking to better understand the safety of mesh used for stress urinary incontinence (SUI) by leveraging electronic health record data. There remains uncertainty with regards to longer term outcomes among women receiving mesh slings for stress urinary incontinence. For this reason, the FDA has partnered with NEST to conduct a multi -site observational postmarket surveillance of women receiving these devices for SUI, with a particular emphasis on outcomes extending beyond one year. This project phase seeks to address knowledge gaps for mid- and long-term outcomes among mesh implantations by leveraging electronic health record data across 5 participating health systems. The FDA intends on incorporating these data into its growing portfolio of evidence in order to help support regulatory decision making on level of risk for these procedures and recommendations around use of mesh for this indication. This study has the potential to increase medical knowledge regarding these devices.

Aggregated and fully de-identified data will be transmitted back to other participating performance sites so that summary statistics can be calculated for all sites. There are minimal potential risks to the human subjects. The study proposes to examine electronic medical records of patients. Patients will not be exposed to study materials or protocols; only electronic medical records will be abstracted retrospectively with the IRB approval in place. Though there is a slight risk of loss of confidentiality or privacy of these subjects, all data will reside within the hospital firewall. The proposed study does not involve any interventions or alternative treatments.

This study adds little to no additional risk to population of interest. Confidentiality of protected health information (PHI) will be assured by maintaining patient records within the hospital firewall and on an encrypted, secure server used by the hospital information systems for clinical duties. The data will be stored in a secure computing environment, encrypted, and with limited log-in access by study personnel. The same safeguards in place for routine clinical care and PHI will always be maintained for this study. Because we will be working within the electronic medical records, we will not have any data to dispose.

